5.4. Dosage and Administration of TAF (Part B, Cohorts 6 - 8)

Part B of this study may enroll up to 3 cohorts of approximately 8 unique subjects per cohort. All subjects will be enrolled after the completion of screening procedures and following confirmation of study eligibility. Within each Cohort (n=8) in Part B, subjects will be enrolled to receive active oral TAF.

A single dose of TAF will be administered orally on Day 1.

Cohort	Treatment
6	200 mg TAF
7	Up to 600 mg TAF
8	Up to 600 mg TAF

The Sponsor may elect to hold dosing, or stop study enrollment at any time based on review of preliminary safety and PK data.

The doses to be evaluated in Cohorts 7-8 will be determined based on cumulative safety (through at least Day 14), available PK and viral kinetic data from previous cohorts. Selected doses will be either lower than, or no more than 3-fold higher than, previously evaluated doses in this study. Cohorts 7 and 8 may be run in parallel.

Observed TAF dosing is required at Day 1.

5.5. Prior and Concomitant Medications

The following medications are excluded while subjects are participating in **Part A**:

- Any prescription medications and over-the-counter medications, including herbal products, with the exception of vitamins, and/or acetaminophen and/or ibuprofen and/or hormonal contraceptive medications. However, the short-term use of topical hydrocortisone cream or A&D ointment to treat minor skin irritation due to ECG leads will be allowed. If a subject requires use of a disallowed medication, a request for such use must be reviewed by the Sponsor and if approved, subjects may continue to participate in the study.
- Any and all illegal or illicit drug use, including use of prescription drugs outside the care of the prescribing physician.

For Part A, if a subject discontinues B/F/TAF between the Day 10 and Day 225 visits, they can switch to an alternative ARV regimen, which should not contain the following prohibited ARVs:

Prohibited ARVs	HIV Protease Inhibitors
	RTV or COBI containing regimens
	Efavirenz
	Etravirine
	Nevirapine

The following medications are excluded while subjects are participating in **Part B**:

- TAF is a substrate of P-glycoprotein (Pgp) and breast cancer resistance protein (BCRP) transporters {DESCOVY® 2017}. Drugs that inhibit or induce Pgp or BCRP activity may lead to increases or decreases, respectively, in TAF absorption. In vitro data suggest TAF may inhibit or induce CYP3A at doses up to 600 mg, however, given its short half-life and transient exposure, clinically relevant changes in CYP3A substrates are not expected following co-administration with a single dose TAF.
- Medications that are potent inhibitors or inducers of Pgp/BCRP are prohibited, and use of herbal/natural supplements are excluded while subjects are participating in this study. Table 5-1 contains examples of medications that are to be excluded while subjects are participating in the study in Part B. As this table is not exhaustive, all concomitant medications are to be reviewed with the sponsor until Day 10. After Day 10, the investigator should follow the current USPI for B/F/TAF {BIKTARVY® 2018}.
- Any and all illegal or illicit drug use, including use of prescription drugs outside the care of the prescribing physician, are prohibited.

Table 5-1. List of medications that are prohibited due to the potential for drug-drug interaction with TAF

Medication Class	Disallowed Medications
Anti-arrhythmics	Amiodarone, Dronedarone, Propafenone
Anti-anginal agents	Ranolazine
Anti-biotics	Clarithromycin
Anti-convulsants	Carbamazepine, Oxcarbazepine, Phenobarbital, Phenytoin
Anti-fungals	Itraconazole
Anti-malarials	Quinidine
Anti-mycobacterials	Rifapentine, Rifabutin, Rifampin
Anti-retroviral agents	Any antiretroviral drug that is not part of the study regimen
Beta blockers	Carvedilol
Ca channel blockers	Verapamil
Herbal/Natural Supplements	St. John's Wort, Echinacea, Milk thistle (i.e., silymarin), Chinese herb sho-saiko-to (or Xiao-Shai-Hu-Tang)

5.6. Dispensing, Accountability, and Disposal or Return of GS-6207 and TAF (study drugs) and B/F/TAF

The investigator (or designee, eg, study center pharmacist) will acknowledge receipt of the study drugs and B/F/TAF (after reviewing the shipment's content and condition) from Gilead (or designee). The investigator will maintain an accurate inventory of all study drug and B/F/TAF. The study drug will be administered at the study center by qualified study center staff. The dose of study drug administered to subjects in the clinic under the supervision of staff will be accurately recorded on the Study Drug Accountability form provided by Gilead (or on equivalent documentation maintained by the study center), which indicates the date and quantity of each dosage formulation dispensed to individual subjects.

Where possible, study drug and B/F/TAF should be destroyed at the site. If the site does not have acceptable procedures in place for drug destruction, arrangements will be made between the site and Gilead Sciences (or Gilead Sciences' representative) for return of unused study drug supplies and B/F/TAF. The study monitor will provide instructions for return.

The study monitor will evaluate each study center's study drug disposal procedures and provide appropriate instruction for destruction of unused study drug supplies. If the site has an appropriate standard operating procedure (SOP) for drug destruction as determined by Gilead, the site may destroy used (empty or partially empty) and unused study drug supplies in accordance with that site's approved SOP. A copy of the site's approved SOP will be obtained for central files.

If study drug or B/F/TAF is destroyed on site, the investigator must maintain accurate records for all drug destroyed. Records must show the identification and quantity of each unit destroyed, the method of destruction, and the person who disposed of the drugs. Upon study completion, copies of the study drug accountability records must be filed at the site. Another copy will be returned to Gilead. Refer to the Pharmacy Binder for study drug disposal/return instructions. The study monitor will review study drug supplies and associated records at periodic intervals.

6. STUDY PROCEDURES

The study procedures to be conducted for each subject enrolled in the study are presented in tabular form in [Appendix 2](#) and described in the text that follows. Additional information is provided in the study procedures manual.

The investigator must document any deviation from protocol procedures and notify the sponsor or contract research organization (CRO).

6.1. Subject Enrollment and Treatment Assignment

Entry into screening does not guarantee enrollment into the study. In order to manage the total trial enrollment, Gilead, at its sole discretion, may suspend screening and/or enrollment at any site or trial-wide at any time.

6.2. Pretreatment Assessments

6.2.1. Screening Visit

Subjects will be screened within 42 days prior to Day 1 to determine eligibility for participation in the study. The following will be performed and documented at screening:

- Obtain written informed consent
- Obtain medical history including history of HIV-1 disease-related events and prior medications within 42 days of the screening visit
- Complete physical examination (urogenital/anorectal exams will be performed at the discretion of the Investigator)
- Vital signs measurement (blood pressure, pulse, respiration rate, and temperature)
- 12-lead ECG performed supine
- Height and Weight
- Obtain blood and urine samples as described in [Section 6.6](#)
- Review of AEs and concomitant medications

Once eligibility is confirmed, each subject will be assigned a unique subject number. Once a subject number has been assigned to a subject, it will not be reassigned to any other subject. Prior to or during the Day 1 visit in **Part A** the Investigator or designee will enroll the subject using the Interactive Web Response System (IWRS). In **Part B**, the Investigator will contact Gilead Sciences to obtain the subject number. The subject number assignment may be performed up to 7 days prior to the in-clinic Day 1 visit provided that all screening procedures have been completed and subject eligibility has been confirmed.

Subjects meeting all of the inclusion criteria and none of the exclusion criteria will return to the clinic within 42 days after screening for Day 1 assessments. **Subjects will be instructed to fast overnight (≥ 6 hours) prior to the Day 1 visit.**

From the time of obtaining informed consent through the first administration of investigational medicinal product, record all serious adverse events (SAEs), as well as any adverse events related to protocol-mandated procedures on the adverse events case report form (eCRF). All other untoward medical occurrences observed during the screening period, including exacerbation or changes in medical history are to be captured on the medical history eCRF. See Section 7 Adverse Events and Toxicity Management for additional details.

6.3. Treatment Assessments

Subjects will be required to visit the clinic on Days 1, 2, 3, 4, 5 (Part B only, if possible), 6 (Part B only, if possible), 7, 8, 9, 10, 14, 29, 43, 57, 85, 113, 141, 169, 197 and 225.

Subjects will be required to fast overnight (≥ 6 hours) prior to visit on Days 1, 3, 7, 10, 85, 169, and 225 for laboratory analyses.

6.3.1. Day 1

The following procedures are to be completed at the Day 1 visit prior to study drug dosing.

- Review of AEs and changes in concomitant medications
- Complete physical examination (urogenital/anorectal exams will be performed at the discretion of the Investigator)
- Vital signs measurement (blood pressure, pulse, respiration rate, and temperature)
- Weight
- 12-lead ECG performed supine (pre-dose)
- Obtain blood and urine samples as described in Section 6.6 (Note: all blood and urine samples should be collected pre-dose on Day 1, except for PK samples as noted in Section 6.6)
- **Part B:** A single dose of TAF will be administered orally on Day 1 at the study center under fasted conditions, with 240 mL of water following an overnight fast (no food or drink, except water, for at least 6 hours).

On Day 1, subjects will be restricted from food intake until after collection of the 4-hour blood draw. Additionally, subjects will be restricted from water consumption 1 hour before and 2 hours after dosing, except for the 240 mL of water given with the study drug. Subjects will fast until 2 hours after study drug administration. Water may be freely consumed following the 2-hour blood draw and for the remainder of the collection period. Subjects may eat after the 4 hour post-dose blood draw.

6.3.2. Assessments on Days 2, 3, 4, 7, 8, 9, 10, 14, 29, 43, 57, 85, 113, 141, 169, 197 and 225

Subjects will be required to fast overnight (≥ 6 hours) prior to visit on Days 3, 7, 10, 85, 169 and 225 for laboratory analyses. Study visit Days 29, 43, 57, 85, 113, 141, 169 and 197 may be completed within ± 2 days of the protocol-specified visit date.

The following procedures are to be completed at all visits unless otherwise specified:

- Review of AEs and changes in concomitant medications
- Symptom directed physical examination
- Vital signs measurement (blood pressure, pulse, respiration rate, and temperature)
- Weight
- 12-lead ECG performed supine (Days 2, 10, 29, 57, 85, 169 and 225)
- Obtain blood and urine samples as described in Section 6.6

6.4. Early Study Discontinuation Assessments

If a subject discontinues their participation prior to Day 225, Early Termination Visit should be performed.

However, if there are any abnormal laboratory results indicating that there is a possible or probable causal relationship with the study drug, every attempt should be made to keep the subject in the study and repeat those laboratory tests weekly (or as often as deemed prudent by the Investigator) until the abnormality is resolved, returns to baseline, or is otherwise explained. If this is not possible or acceptable to the subject or investigator, the subject may be withdrawn from the study.

The following evaluations should be performed at the Early Termination Visit:

- Review of AEs and changes in concomitant medications
- Complete physical examination (urogenital/anorectal exams will be performed at the discretion of the Investigator)
- Vital signs measurement (blood pressure, pulse, respiration rate, and temperature)
- Weight
- Obtain blood and urine samples as described in Section 6.6
- Counsel subject regarding the importance of continuing a complete ARV therapy in accordance to standard of care, and refer patient to an appropriate HIV treatment facility

6.5. Criteria for Discontinuation of Study

Study may be discontinued in the following instances:

- Intercurrent illness that would, in the judgment of the investigator, affect assessments of clinical status to a significant degree. Following resolution of intercurrent illness, the subject may resume study dosing at the discretion of the investigator.
- Unacceptable toxicity, or toxicity that, in the judgment of the investigator, compromises the ability to continue study-specific procedures or is considered to not be in the subject's best interest
- Subject request to discontinue for any reason
- Subject noncompliance with B/F/TAF
- Pregnancy during the study; refer to [Appendix 6](#) and [Appendix 7](#)
- Discontinuation of the study at the request of Gilead, a regulatory agency or an institutional review board or independent ethics committee (IRB/IEC)

6.6. Clinical Laboratory Assessments

Blood and urine samples will be collected throughout the study as outlined below, within Section 6, and in [Appendix 2](#) Study Procedures Table.

6.6.1. Blood Samples

- Blood sample collection for the following laboratory analyses will be performed at every visit, unless specified:
 - Serum pregnancy test (females of childbearing potential only). If the test is positive, the subject will not be randomized (**Screening and Days 29, 57, 85, 113, 141, 169, 197 and 225**)
 - Serum FSH test (required for female subjects who have stopped menstruating for ≥ 12 months but do not have documentation of ovarian hormonal failure) (**Screening only**)
 - Urine pregnancy test (females of childbearing potential only). If the test is positive, confirmatory serum test should be sent and study drug dosing should be delayed until results obtained (**Day 1**)
 - Chemistry profile: alkaline phosphatase, AST, ALT, GGT, total bilirubin, direct and indirect bilirubin, total protein, albumin, LDH, CPK, bicarbonate, BUN, calcium, chloride, creatinine, glucose, phosphorus, magnesium, potassium, sodium, uric acid, amylase (reflex lipase testing is performed in subjects with total amylase $> 1.5 \times \text{ULN}$) (**All visits except Days 2, 4, 8 and 9**). Subjects will be required to fast overnight (≥ 6 hours) prior to visit on Days 3, 7, 10, 85, 169 and 225.
 - Estimated glomerular filtration rate according to the Cockcroft-Gault formula for Creatinine clearance (**All visits except Days 2, 4, 8 and 9**)
Male:
$$\frac{(140 - \text{age in years}) \times (\text{wt in kg})}{72 \times (\text{serum creatinine in mg/dL})} = \text{CLcr (mL/min)}$$

Female:
$$\frac{(140 - \text{age in years}) \times (\text{wt in kg}) \times 0.85}{72 \times (\text{serum creatinine in mg/dL})} = \text{CLcr (mL/min)}$$
 - Hematology profile: complete blood count (CBC) with differential and platelet count (**All visits except Days 2, 4, 8 and 9**)
 - CD4+ cell count (**Screening and Days 1, 10, 29, 43, 57, 85, 113, 141, 169, 197 and 225**)
 - Plasma HIV-1 RNA. Any subsequent HIV-1 genotype and phenotype testing will be performed as described in Section 6.7.
 - HIV-1 genotype and phenotype for PR, RT, IN, and capsid (**Screening only**)
 - HIV-1 capsid genotype and phenotype (**Day 10**)
 - HIV DNA genotyping (**Days 85, 169 and 225**)

- Hepatitis B virus (HBV) serologies (HBV surface antigen, HBV core antibody, HBV surface antibody) (**Screening only**)
- Hepatitis C virus (HCVAb) serology (**Screening only**)

CCU [REDACTED]

- Plasma storage samples for safety and virology testing (HIV-1 capsid genotype and phenotype) (**Not collected at Screening visit**)

GS-6207 PK Sampling (Part A, Cohorts 1 – 5)

- Blood samples to determine PK in plasma:
 - The exact time of study drug administration and the exact time points (date and 24-hour clock) of collection of plasma samples must be carefully recorded.
 - **Day 1:** Time 0 (pre-dose), 1, 2, 4, 8, 12 and 24 hours post dose (relative to study drug dosing time) blood sample collection to determine pharmacokinetics (PK) in plasma on Day 1
 - **Days 3, 4, 7, 8, 9, 10, 14, 29, 43, 57, 85, 113, 141, 169, 197 and 225:** a single anytime PK sample will be collected.

TAF PK sampling (Part B, Cohorts 6 - 8):

- Plasma PK samples will be collected to determine PK of TAF and its metabolite, TFV, at the following time points relative to study drug dosing:
 - **Day 1:** 0 (pre-dose), 0.5, 1, 2, 3, 4, 6, 8, 10, 12, 24 and 48 hours post dose.
 - **Days 4, 5 (if possible), 6 (if possible), 7, 8, 9, and 10** at approximately the same time in the morning as pre-dose on Day 1.
- PBMC PK samples will be collected to determine PK of TFV-DP at the following time points relative to study drug dosing:
 - **Day 1:** 0 (pre-dose), 1, 2, 4, 6, 8, 12, 24 and 48 hours post dose.
 - **Days 4, 5 (if possible), 6 (if possible), 7, 8, 9, and 10** at approximately the same time in the morning as pre-dose on Day 1.

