The Sponsor may elect to hold dosing, or stop study enrollment at any time based on review of preliminary safety and PK data.

The doses to be evaluated in Cohorts 7-8 will be determined based on cumulative safety (through at least Day 14), available PK and viral kinetic data from previous cohorts. Selected doses will be either lower than, or no more than 3-fold higher than, previously evaluated doses in this study. Cohorts 7 and 8 may be run in parallel.

Observed TAF dosing is required at Day 1.

In Part A, following screening and Day 1 visits, subjects will be required to visit the clinic on Days 2, 3, 4, 7, 8, 9, 10, 14, 29, 43, 57, 85, 113, 141, 169, 197 and 225.

In Part B, following screening and Day 1 visits, subjects will be required to visit the clinic on Days 2, 3, 4, 5 (if possible), 6 (if possible), 7, 8, 9, 10, 14, 29, 43, 57, 85, 113, 141, 169, 197 and 225.

Adverse events, concomitant medications, complete or symptom-directed physical examinations, and HIV-1 RNA will be performed at Screening, Day 1, and all subsequent study visits. CD4+ cell count will be performed at Screening, Day 1, Day 10, and all subsequent study visits. Other laboratory analyses (hematology, chemistry, and urine chemistry) will be performed at Screening, Days 1, 3, 7, 10, 14, and all subsequent study visits. Fasting is required for laboratory analyses at Days 1, 3, 7, 10, 85, 169 and 225. ECGs will be performed at Screening, Days 1 (pre-dose), 2, 10, 29, 57, 85, 169, and 225.

A plasma sample for genotypic and phenotypic testing of HIV-1 capsid (Part A) or HIV-1 RT (Part B) will be collected at Screening and Day 10 for all subjects to determine eligibility and to evaluate the potential emergence of resistance against GS-6207 (Part A) or TAF (Part B). The screening plasma sample will also be used for genotypic testing of HIV-1 PR, RT, and IN to determine eligibility.

A whole blood sample for potential HIV DNA genotyping will be collected at Days 85, 169 and 225.

CCI
[REDACTED]

Subjects who meet the criteria for virologic failure after Day 10 will be tested for the potential development of resistance against all components of the treatment regimen, including GS-6207.

GS-6207 PK sampling (Part A, Cohorts 1 –5):

Blood samples will be collected to determine GS-6207 PK (and metabolites, if applicable) in plasma at the following time points relative to study drug dosing:

- Day 1: 0 (pre-dose), 1, 2, 4, 8, 12, and 24 hours post dose.

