3. STUDY DESIGN

3.1. Endpoints

The primary endpoint is the maximum reduction of plasma HIV-1 RNA (\log_{10} copies/mL) from Day 1 through Day 10.

Secondary endpoints include:

- Incidences of adverse events and graded laboratory abnormalities
- PK parameters of GS-6207 (Part A) and TAF (and its metabolites, as appropriate) (Part B)
- Correlation between C_t (concentration at Day 10) of GS-6207 (Part A) and the maximum reduction of plasma HIV-1 RNA (\log_{10} copies/mL) from Day 1 through Day 10
- Number and percentage of subjects ever achieving HIV-1 RNA < 50 copies/mL by Day 10 (Part A)
- Incidences of any emergence of CAI resistance (Part A)
- Incidences of any emergence of TAF resistance (Part B)

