8.5.2. Secondary Analyses

Correlation between C_t of GS-6207 and the maximum reduction of HIV-1 RNA (\log_{10} copies/mL) from Day 1 through Day 10 will be assessed using the Pearson correlation analysis. Analysis will be done for each treatment group.

The percentage of subjects ever achieving HIV-1 RNA < 50 copies/mL by Day 10 (for Part A only) will be summarized by treatment group. Fisher exact test will be used for comparison between treatment groups.

Percentage of subjects with any emergence of CAI resistance and TAF resistance, respectively, will be summarized by treatment group.

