- d Within 72 hours of permanently discontinuing study. Counsel subject regarding the importance of continuing a complete ARV therapy in accordance to standard of care, and refer patient to an appropriate HIV treatment facility.
- e Females of childbearing potential only
- f Hematology: CBC with differential and platelet count
- g Chemistries: Alkaline phosphatase, AST, ALT, GGT, total bilirubin, direct and indirect bilirubin, total protein, albumin, LDH, CPK, bicarbonate, BUN, calcium, chloride, creatinine, glucose, phosphorus, magnesium, potassium, sodium, uric acid, and amylase (reflex lipase testing if total amylase > 1.5 × ULN).
- h Fasting overnight (≥ 6 hours) required for Days 1, 3, 7, 10, 85, 169 and 225

- i FSH test is required for female subjects who have stopped menstruating for ≥ 12 months but do not have documentation of ovarian hormonal failure.
- j Vital signs – blood pressure, pulse, respiration rate, and temperature, weight
- k Urinalysis and Urine Chemistry: including color & clarity, specific gravity, pH, glucose, ketones, bilirubin, urobilinogen, blood, nitrite, leukocyte esterase and microscopic (if microscopic elements are seen), urine protein, albumin, creatinine, phosphate, calcium, magnesium and uric acid
- l Part A: Serial blood samples to determine pharmacokinetics (PK) in plasma will be collected at the following time points relative to study drug dosing 0 (pre-dose), 1, 2, 4, 8, 12 and 24 hours post dose.
[REDACTED]
- n Part A: Single Anytime PK sample to be collected at the Day 3, 4, and 7 through 225 visits.
- o Part B: Plasma PK samples to be collected at the following time points relative to study drug dosing: 0 (pre-dose), 0.5, 1, 2, 3, 4, 6, 8, 10, 12, 24 and 48 hours post dose; as well as at Days 4, [REDACTED] 7, 8, 9 and 10 at approximately the same time in the morning as pre-dose on Day 1.
- p Part B: PBMC PK samples to be collected at the following time points relative to study drug dosing: 0 (pre-dose), 1, 2, 4, 6, 8, 12, 24 and 48 hours post dose, as well as at Days 4, [REDACTED], 7, 8, 9 and 10 at approximately the same time in the morning as pre-dose on Day 1.
[REDACTED]
- r Part A: subjects require the HIV-1 capsid genotype/phenotype to confirm eligibility prior to randomization. Part B: the capsid genotype/phenotype will be completed for informational purposes, but it is not be required to confirm eligibility.

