### **Schedule of Assessments**

In Part A, following screening and Day 1 visits, subjects will be required to visit the clinic on Days 2, 3, 4, 7, 8, 9, 10, 14, 29, 43, 57, 85, 113, 141, 169, 197, and 225.

In Part B, following screening and Day 1 visits, subjects will be required to visit the clinic on Days 2, 3, 4, 5 (if possible), 6 (if possible), 7, 8, 9, 10, 14, 29, 43, 57, 85, 113, 141, 169, 197, and 225.

For both Part A and Part B, adverse events (AEs), concomitant medications, complete or symptom-directed physical examinations, and HIV-1 RNA will be performed at Screening, Day 1, and all subsequent study visits. CD4 cell count will be performed at Screening, Day 1, Day 10, Day 29, and all subsequent study visits. Other laboratory analyses (hematology, chemistry, and urine chemistry) will be performed at Screening, Days 1, 3, 7, 10, 14, and all subsequent study visits. Fasting is required for laboratory analyses at Days 1, 3, 7, 10, 85, 169, and 225. ECGs will be performed at Screening, Days 1 (predose), 2, 10, 29, 57, 85, 169, and 225.

Additionally, in Part A, blood samples will be collected for genotypic and phenotypic testing of HIV-1 capsid and for determining PK of LEN. In Part B, blood samples will be collected for genotypic and phenotypic testing of HIV-1 reverse transcriptase (RT) and for determining PK of TAF and tenofovir (TFV). In Part B, the peripheral blood mononuclear concentration (PBMC) PK samples will be collected to determine PK of tenofovir diphosphate (TFV-DP).

Details regarding study procedures could be found in [Appendix 1](#).

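### The synopsis schedules Day 10 RT resistance testing in Part B, but the procedure sections give capsid only; the SAP also omits the protocol's resistance summary without declaring it

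*Protocol*

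**What the plan says.** Protocol 3.1 lists as a secondary endpoint "Incidences of any emergence of TAF resistance (Part B". It also lists capsid inhibitor (CAI) resistance for Part A.

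The synopsis ties sampling to these endpoints. Its sentence on resistance sampling reads, in part: "genotypic and phenotypic testing of HIV-1 capsid (Part A) or HIV-1 RT (Part B) will be collected at Screening and Day 10". This applies to every subject and is meant partly to look for emerging resistance to the drug of each part.

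Protocol 6.6.1 says something else. It lists "HIV-1 genotype and phenotype for PR, RT, IN, and capsid (Screening only", and then "HIV-1 capsid genotype and phenotype (Day 10", with no split between Part A and Part B. The storage line reads "Plasma storage samples for safety and virology testing (HIV-1 capsid genotype and phenotype". Any later genotyping is referred to Section 6.7, which deals only with virologic failure after B/F/TAF has begun.

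In the Appendix 2 table, the general genotyping row is marked at Screening only and the capsid row at Screening and Day 10. Footnote r adds: "Part B: the capsid genotype/phenotype will be completed for informational purposes". SAP Appendix 1 reproduces the same rows. SAP 1.2 states "In Part B, blood samples will be collected for genotypic and phenotypic testing of HIV-1 reverse transcriptase (RT" but gives no day.

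On analysis, Protocol 8.5.2 says: "Percentage of subjects with any emergence of CAI resistance and TAF resistance, respectively, will be summarized by treatment group". SAP 1.1 keeps both resistance objectives. SAP Section 6 contains no resistance analysis, and SAP 6.4 declares only one change, the dropped comparison of TAF with the Part A placebo group.

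**The concern.** A single oral dose of TAF followed by monotherapy up to Day 10 is the exposure in which TAF resistance might emerge, and Protocol 1.6 names that risk. To observe it, RT must be sequenced at the end of that window. Capsid sequence says nothing about resistance to an RT inhibitor.

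Protocol Sections 6 and 6.6 direct the reader to Section 6 and Appendix 2 for what to do at each visit. If those are followed, the Part B Day 10 sample is tested for the wrong gene for this endpoint. If the SAP is then followed, no resistance table is produced for either part. A report could state that no resistance was observed without showing how many subjects were tested.

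The stakes are somewhat higher because SAP 1.2 reports that Cohorts 6 and 7 did not show lasting antiviral activity over 10 days. Whether RT mutations emerged is relevant to interpreting that.

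**Working it through.** No power, alpha or event calculation applies. The check sets the passages side by side.

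**Step 1. When is RT tested in Part B?**

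| Place | RT | Resistance test on Day 10 |
|---|---|---|
| Protocol synopsis | Screening and Day 10 | RT for Part B, capsid for Part A |
| Protocol 6.6.1, genotype lines | Screening only | Capsid, both parts |
| Protocol 6.6.1, plasma storage line | Not named | Capsid is the only virology use named |
| Protocol Appendix 2 table | General genotyping at Screening only | Capsid row only |
| Protocol Appendix 2, footnote r | No RT counterpart | Footnote to the capsid row; Part B capsid testing is informational |
| SAP 1.2 | Collected in Part B, no day given | Not stated |
| SAP Appendix 1 table | General genotyping at Screening only | Capsid row only |

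The synopsis is the only place that schedules Day 10 RT testing. Section 6.6.1 and both tables are incompatible with it. Footnote r shows that Part B was considered when the capsid row was written, yet no RT row was added.

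**Step 2. Can other post-dose data fill the gap?**

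- *Failure-triggered testing (Protocol 6.7).* RT is tested only once virologic failure on B/F/TAF is confirmed. Suboptimal response is judged at Day 57, which is 57 − 10 = 47 days after B/F/TAF starts. Rebound can be flagged earlier, but it too is defined after that start.
- *HIV DNA genotyping.* Blood is drawn on Days 85, 169 and 225. The earliest is 85 − 10 = 75 days after B/F/TAF starts. The synopsis describes the genotyping as only potential, and no gene is named.

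B/F/TAF itself contains TAF, so neither source isolates emergence during the monotherapy window. The first is also confined to subjects who fail.

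- *Stored plasma.* Appendix 2 schedules a storage sample at every visit after Screening, including Day 10. Material may therefore exist, although 6.6.1 names only capsid as its virology use.

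**Step 3. How many subjects?** The protocol plans about 8 per Part B cohort, so 3 × 8 = 24 over three cohorts. SAP 1.2 says Cohort 8 did not enroll, which leaves 2 × 8 = 16 planned. Neither document gives the actual number enrolled, and Protocol 4.1 allows replacements.

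**Step 4. Is resistance analysed?** SAP 6.2 defines one secondary efficacy endpoint, HIV-1 RNA below 50 copies/mL by Day 10. SAP 6.3 adds change in HIV-1 RNA, the by-visit percentage below 50 copies/mL and change in CD4 count. No resistance definition, denominator or table appears there or in the SAP table of contents for Section 6. Other departures are declared: the placebo comparison in 6.4 and the replaced correlation in 8.3.3. This one is not, and it affects CAI resistance in Part A as well as TAF resistance in Part B.

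**The case against.** The best reply is that the plan does schedule the data. The synopsis says plainly that Part B subjects have RT tested on Day 10, and SAP 1.2 lists RT testing in Part B. That stands. A reader of 6.6.1 alone might infer that TAF resistance has no scheduled post-dose assessment at all, and the documents do not support that. The defect is a contradiction between parts of the protocol. Nothing shows a decision to leave the test out.

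A reader might also infer that the incidence will be reported as zero because nobody was tested. That would need the synopsis to be ignored and untested subjects to be counted as negative; neither document says either. Nor do the documents show that 16 subjects went untested, since 16 is a planned size.

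It can also be said that Protocol Section 6 refers to a study procedures manual, and that the sponsor provides the screening genotype reports. The Day 10 assay may be set correctly in laboratory instructions outside these documents. Redacted lines in 6.6.1 and Appendix 2 could in principle hide an RT entry, although the visible text restricts RT to Screening and the synopsis sentence is not redacted. These points make the loss of data a risk and not a fact. They do not remove the contradiction.

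Finally, this is a descriptive secondary endpoint in a proof-of-concept study, and the primary endpoint is untouched. That limits the reach of the problem, but it does not explain an undeclared omission from the SAP.

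**Conclusion.** The point holds as two linked errors.

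1. Protocol 6.6.1 with its storage line, Protocol Appendix 2 and SAP Appendix 1 contradict the synopsis on Day 10 resistance testing in Part B. Followed as written, they would leave a Part B secondary endpoint unmeasured in the monotherapy window for every subject, at about 8 planned per cohort. The later samples do not replace the missing result.
2. The SAP keeps the CAI and TAF resistance objectives but omits the summary that Protocol 8.5.2 specifies, without declaring the change.

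The first conclusion assumes that sites and the laboratory work from Section 6 and Appendix 2, as the protocol directs, and that no unseen manual or redacted line corrects them. The second rests on the visible SAP text; its table of contents for Section 6 shows no redaction and no resistance section.

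**What to change.** - **Protocol.** Make the Day 10 line of 6.6.1 and the Day 10 entry in Appendix 2 read capsid for Part A and RT for Part B, as in the synopsis. Extend the storage line to RT for Part B. Correct SAP Appendix 1 to match.
- **Samples already taken.** The SAP describes the Part B cohort decisions and interim analyses in the past tense, so a text correction alone may come too late to create data. Confirm whether Day 10 RT was run. If it was not, assay stored Day 10 plasma where consent and sample handling permit.
- **SAP.** Add to Section 6 the percentage of subjects with emergent CAI or TAF resistance by treatment group, as in Protocol 8.5.2. Show the number of subjects with a post-dose result as the denominator, so that absence of resistance can be told from absence of testing. That denominator is a recommendation beyond the protocol's wording. Alternatively, declare and explain the removal in SAP 6.4.

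The cost is a protocol clarification, a corrected SAP schedule table and a short descriptive summary. No extra visit or blood draw is needed, because Day 10 plasma is already scheduled. Any real expense is the RT assay on Part B samples, if it has not been done.
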